## **2. Schedule of Activities**

## Study Schedule Protocol I8F-MC-GPHI

	Screening	Treatment Periods 1 to 3 Study Days (≥35 days washout between Day 1 doses)											ED c	Comments
Procedure	D-28 to D-2	D-1 b	D1	D2	D3	D4	D5	D6	D7	D8	D15	D21	D36 (±1) b	
Informed Consent	X													
Subject Admission to CRU		X												
Subject Discharge from CRU									X					Subjects' CRU stay may be extended at the investigator's discretion for safety monitoring.
Outpatient Visit	X									X	X	X	X	
Tirzepatide Dosing		0 hour												Study drug will be administered after an overnight fast of at least 8 hours.
Medical History	X													
Physical Examination /Medical Assessment	X	X							X		X	X		Full physical examination at screening. Thereafter, targeted reviews and medical assessments as appropriate.
Weight and Height	X	X									X	X		Height is required to be taken at screening only.
Temperature	X	Predose												
Safety 12-Lead ECG (hours postdose) a	X	Predose	24		72				X			X	X	Single safety ECGs will be collected. ECGs must be recorded before collecting any blood samples. Subjects must be supine for approximately 5 to 10 minutes before ECG collection, and remain supine but awake during ECG collection.
Supine Vital Signs (hours postdose) a	X	Predose, 12	24	48	72				X	X	X	X	X	Additional time points may be added, if warranted and agreed upon between Lilly and the investigator.
Clinical Laboratory Tests	X	X							X	X	X	X	X	See Appendix 2 for details. Subjects will be fasted at least 8 hours before sampling.
Urine Drug Screen	X	X												
Alcohol Breath Test		X												
Pregnancy Test	X	X									X	X		Female subjects only. See Appendix 2 for details.
AEs/Concomitant Medications	X	X	X	X	X	X	X	X	X	X	X	X	X	
Waist, Upper Arm, and Thigh Circumference and Skinfold Thickness		X												Circumference of the injection site for the specific period should be measured in triplicate and the mean recorded. Waist circumference is measured for the abdomen injection site.
Fat Deposition Assessment at Injection Site - DEXA Scan		X												DEXA scan of the relevant injection site may be performed any time between Day -4 and Day -1.
Pharmacogenetic Sample a		Predose												Single sample in Treatment Period 1 only.

	Screening	Treatment Periods 1 to 3 Study Days ( $\geq 35$ days washout between Day 1 doses)												ED c	Comments

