### 10.3. Statistical Analyses

Statistical analysis of this study will be the responsibility of Eli Lilly and Company or its designee.

Pharmacokinetic analyses will be conducted on data from all subjects who receive at least one dose of the IP and have evaluable data.

Safety analyses will be conducted for all subjects who receive at least one dose of the IP, whether or not they completed all protocol requirements.

Additional exploratory analyses of the data will be conducted as deemed appropriate. Study results may be pooled with the results of other studies for population PK analysis purposes.

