#### **4.3 Exploratory Objective**

- To explore the relationship between adiposity at injection site with tirzepatide exposure.

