## **9. STATISTICAL METHODOLOGY**

### **9.1 General**

Data listings will be provided for all data that is databased. Summary statistics and statistical analysis will only be presented for data where detailed in this SAP. For continuous data, summary statistics will include the arithmetic mean, arithmetic standard deviation (SD), median, min, max and N; for log-normal data (e.g. the PK parameters: area under the concentration versus time curve [AUC] and maximum observed drug concentration [ $C_{max}$ ]) the geometric mean and geometric coefficient of variation (CV%) will also be presented. For categorical data, frequency count and percentages will be presented. Data listings will be provided for all subjects up to the point of withdrawal, with any subjects excluded from the relevant population highlighted. Summary statistics and statistical analyses will generally only be performed for subjects included in the relevant analysis population. For the calculation of summary statistics and statistical analysis, unrounded data will be used.

Mean change from baseline is the mean of all individual subjects' change from baseline values. Each individual change from baseline will be calculated by subtracting the individual subject's baseline value from the value at the timepoint. The individual subject's change from baseline values will be used to calculate the mean change from baseline using a SAS procedure such as Proc Univariate.

Where specified in the sections below, safety data will be summarised by BMI group (Low, High and Overall) and also by injection site location (Abdomen, Upper Arm and Thigh), but not by injection site within BMI group. For the secondary objective, the PK data will be presented by injection site within BMI group.

Data analysis will be performed using SAS® Version 9.4 or greater.

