The  $t_{\max}$  will be analyzed, analyzed through non-parametric methods for all of the above comparisons. Estimates of the median difference, 90% CIs, and p-values from the Wilcoxon signed rank test will be calculated.

Relationship between exposure to tirzepatide and adiposity/body composition parameters (i.e., skinfold thickness and fat deposition) at the injection sites and waist, thigh, and upper arm circumference may be explored if deemed appropriate. Scatter plots of  $AUC(0-\infty)$  and  $C_{\max}$  versus skinfold thickness, fat percentage, lean mass percentage, waist circumference, thigh circumference, and upper arm circumference will be presented by injection site along with the Pearson's correlation coefficient and the associated p-value.

Additional analyses, such as subgroup analyses, may be carried out if appropriate.

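### The by-site Pearson correlation planned for the exploratory objective describes a marginal association but cannot separate injection-site fat from whole-body size; a weight-adjusted version should sit beside it

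*SAP*

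**What the plan says.** The objective in SAP 4.3 is "To explore the relationship between adiposity at injection site with tirzepatide exposure". The protocol has the same objective in Table GPHI.1.

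SAP 9.3.2 plans scatter plots of AUC(0-∞) and Cmax against "skinfold thickness, fat percentage, lean mass percentage, waist circumference, thigh circumference, and upper arm circumference". These "will be presented by injection site along with the Pearson's correlation coefficient and the associated p-value". No covariate, subject term, significance level or multiplicity rule is attached. The sentence names the two PK parameters without a log, whereas the primary and secondary models in the same section use log-transformed values.

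Other wording leaves room for more but defines nothing:
- The relationship with measures "at the injection sites and waist, thigh, and upper arm circumference may be explored if deemed appropriate" (SAP 9.3.2; protocol 10.3.2.2 is equivalent).
- "Additional analyses, such as subgroup analyses, may be carried out if appropriate" (SAP 9.3.2).
- "Additional exploratory analyses of the data will be conducted as deemed appropriate" (protocol 10.3).
- Protocol 10.2.2 allows weight and BMI to be used as classification variables in PK analyses.

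The secondary model in SAP 9.3.2 adds BMI group and BMI group-by-site, on the log scale with a random subject effect. It contains no local adiposity measure.

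**The concern.** Three features of the design act together. The dose is a fixed 5 mg. BMI is deliberately spread, with about half the high group intended to exceed 35.0 kg/m². Adiposity is compared across subjects within one site. A heavier subject will tend to have more fat at every site and, if exposure falls with body size, a lower AUC and Cmax wherever the injection is given. A by-site correlation then mixes any local absorption effect with body size.

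Two things are at stake. A small p-value could be taken as evidence about local fat when none is there. A real local effect that runs against the body-size effect could be masked. Subjects have skinfold, circumference and DEXA measurements in each period to serve this objective, so it is worth extracting what those data can show.

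**Working it through.** **The plan's own figures.** No power or error rate is stated for the correlations. The only stated power is at least 98% for the primary comparisons with 36 completers. It reproduces when 19.6% is taken as the within-subject CV: σ_W = √ln(1 + 0.196²) = 0.1942, SE = 0.1942 × √(2/36) = 0.0458, two one-sided tests at a ratio of 1.05, power 98.3% (68 df). The same σ_W is used below.

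**Inputs from the documents.** 54 enrolled and at least 36 completing; the BMI bands, half the subjects in each and half the high group above 35.0; CV 19.6%.

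**Assumptions, not in the documents.** Exposure proportional to weight^(−b), with b from 0 to 0.75; correlation ρ of local fat with BMI 0.6 to 0.8; between-subject CV 20% (σ_B = 0.198); BMI uniform within each band; height mean 1.70 m, SD 0.09 m. These imply an SD of log weight s = 0.277 and a correlation of BMI with log weight c = 0.918.

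**Expected correlation with no local effect.** r ≈ −ρ·c·b·s / √(b²s² + σ_B² + σ_W²).
- b = 0.5: b·s = 0.138; denominator √(0.0191 + 0.0392 + 0.0377) = 0.310; r = −0.25 (ρ = 0.6) to −0.33 (ρ = 0.8).
- b = 0.75: b·s = 0.208; denominator √(0.0431 + 0.0392 + 0.0377) = 0.346; r = −0.33 to −0.44.

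The two-sided 5% critical value of |r| is 0.329 at n = 36 and 0.268 at n = 54, so correlations of this size often cross it. Fisher's z gives rejection rates of 30–50% (b = 0.5) and 50–77% (b = 0.75) at n = 36, and 43–68% and 69–92% at n = 54.

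**Simulation with no local effect** (3,000 trials per setting; ranges run over ρ = 0.6 to 0.8; share with p<0.05):

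| n | b | raw Pearson, one site | at least one of 3 sites | log-scale Pearson, one site |
|---|---|---|---|---|
| 36 | 0 | 5% | 14% | 5–6% |
| 36 | 0.25 | 12–17% | 30–38% | 13–18% |
| 36 | 0.5 | 28–48% | 60–80% | 31–52% |
| 36 | 0.75 | 48–78% | 83–97% | 53–82% |
| 54 | 0 | 5% | 14% | 5% |
| 54 | 0.25 | 15–25% | 36–52% | 16–27% |
| 54 | 0.5 | 41–68% | 76–92% | 45–71% |
| 54 | 0.75 | 66–93% | 95–100% | 71–94% |

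In every row, adjusting log exposure for log weight, or using only within-subject variation, gives about 4–6%. Taking logs alone does not help.

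**Sensitivity.** With a between-subject SD of 0.30, and the 0.6–0.8 correlation placed on log weight instead of BMI, one-site rates are 24–38% (b = 0.5) and 41–68% (b = 0.75) at n = 36, and 33–52% and 56–86% at n = 54.

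**With a true local effect** of +6% exposure per SD of fat (b = 0.5, ρ = 0.8), the mean raw r is about −0.15, the wrong sign. Power at p<0.05, by the assumed correlation of fat between sites within the sample:

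| inter-site correlation | n = 36: weight-adjusted, one site | n = 36: within-subject | n = 54: weight-adjusted, one site | n = 54: within-subject |
|---|---|---|---|---|
| 0.64 | 13% | 31% | 17% | 45% |
| 0.80 | 14% | 19% | 17% | 28% |
| 0.90 | 13% | 12% | 17% | 15% |

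**Number of p-values.** Using only the circumference that matches the site, 4 measures × 3 sites × 2 PK parameters = 24; read literally, 6 × 3 × 2 = 36. At 5% each, 1.2 to 1.8 would fall below 0.05 by chance alone.

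**The case against.** The objective asks for a relationship, not for a local effect independent of body size, and a scatter plot with r describes a relationship correctly. No hypothesis, significance level or decision hangs on these p-values; the 0.05 cut-off in the working is mine. The secondary model already looks within subjects at whether BMI group modifies the site effect, and both documents allow further exploratory work. The size of the problem rests on a weight effect that the documents do not give.

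Most of this stands, and it rules out stronger readings that a reader might infer:
- *That the planned analysis is invalid or cannot address the objective.* It does address the marginal association. What it cannot do is attribute that association to local fat.
- *That the trial will report false local effects.* The plan makes no such claim, and with no weight effect there is no inflation.
- *That the missing log is a serious error.* It is inconsistent with the PK models, but SAP 9.1 also reports arithmetic summaries for these parameters, and taking logs barely changes the rates.
- *That a within-subject slope is clearly superior.* Its advantage shrinks as fat at the three sites becomes more correlated, and is gone at 0.90 in the table above.

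The objection does not remove the remaining point. Permission for undefined analyses is not a plan to adjust for body size, and the secondary model has no local measure. A p-value beside r invites a reading that the statistic cannot support.

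**Conclusion.** The point holds in a limited form. The one statistic prespecified for the exploratory objective cannot distinguish adiposity at the injection site from whole-body size. For a weight exponent of 0.5 to 0.75, a given site's correlation would reach p<0.05 with no local effect in about 28–78% of trials at n = 36 and 41–93% at n = 54, against a nominal 5%. At exponent 0 the rate is 5%. These figures depend on the assumed weight effect, the correlation of local fat with BMI and the between-subject variability; the direction was the same for every non-zero exponent tried. Only the exploratory objective is touched: the sample size and the primary and secondary analyses are unaffected. It is a cheap improvement to consider.

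**What to change.** In SAP 9.3.2:

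1. Keep the by-site scatter plots and raw r. Beside each, report the partial correlation of log AUC(0-∞) and log Cmax with the adiposity measure, adjusted for log Day -1 body weight. Weight is repeated on Day -1 in the Schedule of Activities, whose comment limits only the other measurement: "Height is required to be taken at screening only".
2. Label all these p-values descriptive, and state that the raw coefficients do not separate local fat from body size.
3. As a supporting analysis, fit the existing log-scale mixed model (site, period, sequence, random subject) with skinfold thickness or DEXA fat percentage standardised within site and split into the subject's mean and the deviation from it. Report the within-subject slope with a 90% CI. Leave circumferences out of this model, since waist, thigh and upper arm are not one measure.

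The cost is a few lines of SAP text and some extra output, with no new data or visits. There are two drawbacks. The weight-adjusted test has low power because weight and fat are collinear. The within-subject slope assumes the same effect per SD at all three sites and loses its power advantage when fat at the sites is highly correlated. The log scale is for consistency with the other PK models.

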## **9.4 Safety and Tolerability Assessments**

### **9.4.1 Adverse events**

Where changes in severity are recorded in the Case Report Form (CRF), each separate severity of the AE will be reported in the listings, only the most severe will be used in the summary tables. A pre-existing condition is defined as an AE that starts before the subject has provided written informed consent and is ongoing at consent. A non-treatment emergent AE is defined as an AE which starts after informed consent but prior to dosing. A treatment-emergent AE is defined as an AE which occurs postdose or which is present prior to dosing and becomes more severe postdose.

All AEs will be listed. Treatment-emergent AEs will be summarized by BMI group, injection site (including overall), severity and relationship to the study drug. The frequency (the number of AEs, the number of subjects experiencing an AE and the percentage of subjects experiencing an AE) of treatment-emergent AEs will be summarized by BMI group, injection site, Medical Dictionary for Regulatory Activities (MedDRA) version 22.0 system organ class and preferred term. The summary and frequency AE tables will be presented for all causalities and those considered related to the study drug. Any serious AEs will be listed.

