#### 10.3.1. Safety Analyses

##### 10.3.1.1. Clinical Evaluation of Safety

All IP and protocol procedure AEs will be listed and study device complaints, and if the frequency of events allows, safety data will be summarized using descriptive methodology.

The incidence of symptoms at each treatment period will be presented by severity and by association with IP as perceived by the investigator. Symptoms reported to occur prior to enrollment will be distinguished from those reported as new or increased in severity during the study. Each symptom will be classified by the most suitable term from the medical regulatory dictionary.

The number of IP-related SAEs will be reported.

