### **11. CHANGES FROM THE PROTOCOL SPECIFIED STATISTICAL ANALYSES**

There were no changes from the protocol specified statistical analyses.

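### The adverse event summary by treatment period that Protocol 10.3.1.1 specifies is absent from the SAP, and SAP Section 11 declares no changes

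*SAP*

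**What the plan says.** Protocol 10.3.1.1 (Clinical Evaluation of Safety) states: "The incidence of symptoms at each treatment period will be presented by severity and by association with IP as perceived by the investigator". The sentence before it makes the general safety summary conditional: "if the frequency of events allows, safety data will be summarized using descriptive methodology". The by-period sentence carries no such condition.

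SAP 9.4.1 plans two kinds of TEAE summary. The first reads: "Treatment-emergent AEs will be summarized by BMI group, injection site (including overall), severity and relationship to the study drug". In the second, the frequency of "treatment-emergent AEs will be summarized by BMI group, injection site, Medical Dictionary for Regulatory Activities (MedDRA) version 22.0 system organ class and preferred term". Neither is by period. The same section says "All AEs will be listed".

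SAP 9.1 names BMI group and injection site as the factors for safety summaries and adds: "Summary statistics and statistical analysis will only be presented for data where detailed in this SAP". SAP Section 3 gives the SAP precedence over the protocol's statistical section and undertakes to identify substantial differences. SAP Section 11 then reports: "There were no changes from the protocol specified statistical analyses".

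**The concern.** Every subject is meant to receive three doses, one at each site, in successive periods. The protocol's by-period table is the summary that would show whether adverse events become more or less frequent from the first dose to the third. The SAP puts site and BMI group in place of period. Because the SAP supersedes the protocol on statistical matters, the protocol's commitment lapses, and a reader who relies on SAP Section 11 would not know that it had.

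What is at stake is the descriptive safety objective. With sites balanced over periods, any trend over successive doses is spread evenly across the three site columns and disappears from them. The overall column pools all doses and cannot show it either.

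**Working it through.** **Is there a real conflict of text?**

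| Element | Protocol 10.3.1.1 | SAP 9.4.1, summary table | SAP 9.4.1, frequency table |
|---|---|---|---|
| Severity | yes | yes | no |
| Relationship | yes | yes | all-cause and related versions |
| Treatment period | yes | no | no |
| Injection site | not named | yes | yes |
| BMI group | not named | yes | yes |

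Elsewhere in SAP 9.4, period appears only in definitions of baseline (laboratory tests, glucose, vital signs, immunogenicity). It is never a summary factor.

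Two readings could remove the conflict, and neither works.

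- *Treatment period might mean injection site.* The protocol uses the term for Periods 1 to 3 in the Synopsis, the Schedule of Activities, Section 5.1 and Section 9.4.2.1. Site has its own name.
- *Symptoms might not mean adverse events.* The sentence follows the adverse event sentence. Its paragraph goes on to separate pre-enrolment symptoms from new or worsened ones and to code them in the regulatory dictionary, which is TEAE reporting.

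**What does a by-site table hide?** The plan gives no adverse event figure by period, so there is none to reproduce. The following is an illustration with assumed rates.

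Inputs: 54 enrolled (SAP Section 7); 3 periods and 3 sequences (SAP Section 5). Assumptions: the sequences form a 3x3 Latin square (they are not given), with 54/3 = 18 subjects each, and incidence p1, p2, p3 depends on period only.

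Each site is then used by 18 subjects in each period, so

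- expected affected subjects per site = 18 × (p1 + p2 + p3), out of 54;
- expected affected subjects per period = 54 × p1, 54 × p2, 54 × p3.

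| Assumed rates, Periods 1/2/3 | Each site | By period |
|---|---|---|
| 20/20/20% | 18 × 0.60 = 10.8 (20.0%) | 10.8 / 10.8 / 10.8 |
| 10/20/30% | 18 × 0.60 = 10.8 (20.0%) | 5.4 / 10.8 / 16.2 |
| 5/15/40% | 18 × 0.60 = 10.8 (20.0%) | 2.7 / 8.1 / 21.6 |

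The three cases cannot be told apart by site and are plainly different by period.

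**Does dropout change this?** Let each sequence shrink equally to 18, 15 and 12 subjects dosed in Periods 1, 2 and 3 (assumed; 12 is the minimum number of completers per sequence). With rates of 10/20/30%, each site has 18 × 0.10 + 15 × 0.20 + 12 × 0.30 = 1.8 + 3.0 + 3.6 = 8.4 affected subjects out of 18 + 15 + 12 = 45, or 18.7%. All three sites agree, so dropout that is equal across sequences does not distort the site comparison. Only dropout that differs between sequences could.

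**The case against.** The strongest reply is that this is a small departure in a non-inferential table. SAP Section 3 promises to identify only substantial differences, and tabulating a descriptive safety summary by the factor under study is a sensible choice. All adverse events are listed, so a marked rise over periods could be noticed or counted. The detailed tables sit in a shell document that was not supplied and might include a by-period table. Additional analyses are permitted.

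Much of this stands as a limit on size. The shells cannot be excluded, although SAP 9.1 ties summaries to what the SAP details and no by-period one is detailed there. A listing lets someone count, but it does not present incidence with a denominator, which is what the protocol promised. Whether or not the difference is called substantial, SAP Section 11 says there were no changes, and on the text there is one.

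A reader might also draw stronger conclusions that the documents do not support:

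- *The injection-site reaction table in SAP 9.4.7 breaches the protocol in the same way.* It does not. Protocol 10.3.1.2 asks only that these reactions be listed and summarized, without mention of period.
- *Dropout mixes site with period in the planned tables.* That needs dropout that differs between sequences. The gap between 54 enrolled and 36 completers (18/54 = 33%) is an allowance, not a forecast.
- *The plan treats re-exposure as an expected risk and leaves it unexamined.* No objective concerns re-exposure, and the antibody sampling schedule does not state that events should rise. SAP 9.4.13 plans to relate antibody status to adverse events, SAP 9.4.12 lists hypersensitivity follow-up data, and Protocol 9.4.7 provides for review of safety trends. Accumulation is also unlikely: 35 days is seven half-lives of about 5 days, leaving 0.5^7 = 0.8%.

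**Conclusion.** The inconsistency is real. Protocol 10.3.1.1 specifies a by-period summary, the SAP text contains none, and SAP Section 11 does not record the omission. The consequence is that, with sites balanced over periods, the planned by-site tables cannot show a change in adverse event incidence over the three doses. The listings remain.

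The size is modest. Safety is a secondary, descriptive objective, and no primary pharmacokinetic comparison depends on this. The textual conflict needs no assumption beyond taking the SAP text as the guide to the planned tables. The averaging argument assumes balanced sequences, and the rates in the illustration are invented to show the mechanism. They do not predict any event rate in this trial, and they do not imply that a trend would be invisible in all planned output.

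**What to change.** In SAP 9.4.1, add a table of TEAE incidence by Period 1, 2 and 3, by severity and relationship, with the number of subjects dosed in that period as the denominator. Keep the by-site and by-BMI tables as they are.

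If the sponsor prefers to omit the by-period table, amend SAP Section 11 to say that the summary in Protocol 10.3.1.1 is not produced, and why.

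A matching by-period table of injection-site reactions under SAP 9.4.7 would be a reasonable optional extension, not a protocol requirement.

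The cost is one table (two with the extension) from data already collected, plus SAP wording. Design, sample size and data collection do not change.
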